5.1.5 Visit 5 (Week 6 ± 7 days, in-clinic)

The following procedures will be performed at Visit 5:

- Perform and record physical examination.
- Record vital signs. (Measure body temperature, systolic / diastolic blood pressure [BP] and pulse rate).
- Perform WOMAC (sections A-C), using the 5-point Likert scale for the evaluation of the study knee.
- Perform PGA evaluation of the study knee.
- Record AEs.
- Record concomitant medications.
- Review rescue medication use.

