5.1.8 Early Termination Visit

The following procedures will be performed at Early Termination Visit:

- Perform and record physical examination, including weight.
- Record vital signs. (Measure body temperature, systolic / diastolic blood pressure [BP] and pulse rate).
- Perform WOMAC (sections A-C), using the 5-point Likert scale for the evaluation of the study knee.
- Perform PGA evaluations of the study knee.
- Collect blood sample for laboratory assessment.
- Record AEs.
- Obtain information from subject about medical care for knee OA prior to participation in the current study (medical history).
- Record concomitant medications.
- Review, count, and collect rescue medication.

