9.3.1 AE Follow up

All AEs occurring during the study are to be followed up in accordance with good medical practice until they are resolved, stabilized or judged no longer clinically significant or, if a chronic condition, until fully characterized. Any AEs that are considered drug-related (possibly related, definitely related) must be followed for 30 days, or to resolution, or until no improvement is expected, whichever occurs first.

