Clinical benefit will be established by significant improvement on the WOMAC Index 3.1 and the PGA as assessed at Weeks 2, 6, 10, and 12. Safety will be assessed by recording adverse events (through 24 hours post-dose and at all follow up contacts) and physical examination and vitals (Baseline, Weeks 6, and 12), and clinical laboratory tests (Screening and Week 12).

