4. HYPOTHESES AND METHODS

4.1 Primary Hypothesis

Demonstration of an effect of at least some minimum size is considered essential for acceptance of efficacy, and this is defined in the current trial as a greater than 30% responder rate based on review of KOL opinion, literature, and clinical benefit in severely diseased OAK patients. For the primary endpoint of the proportion of patients who are responders to the OMERACT-OARSI criteria from above, the following hypothesis will be tested.

$$H_0:\pi \leq \pi_0 \text{ versus } H_A:\pi > \pi_0$$

Where π_0 is the hypothesized clinically significant value for the proportion of responders. The value will be 30% in this study. This test will be tested using an exact binomial test. That is, given the sample size of n , the number of responders X , and the value of $\pi_0 = 0.30$, then probability that X or more events would be observed will be calculated as the p -value. Since this is a one-sided test, the alpha level will be 0.025.

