4.9 Data presentation

4.9.1 Demographic and Baseline Characteristics:

Demographic (e.g., age, sex, race, and ethnicity) and Baseline characteristics (e.g., weight, height, prior injection of another intra-articular therapeutic for OA of the knee) will be summarized using descriptive statistics, overall and by treatment group for the ITT analysis population. Demographic data for the historic control will be provided and summarized.

4.9.2 Medical History and Physical Examination:

The number and percent of subjects with past and current medical disorders at the time of randomization will be presented overall for the ITT analysis population. Results of any abnormalities documented from the abbreviated physical examination at Baseline and Week 12, will be summarized overall for the safety and ITT analysis populations.

4.9.3 Concomitant Medications or Treatments:

The number and percent of subjects receiving concomitant medications or treatments prior to and during the study and at the final visit will be tabulated and presented overall for the ITT analysis population. Concomitant medications/treatments will be summarized using descriptive statistics and will be presented by type of drug (WHO DRUG classification) overall for the safety and ITT analysis populations. Concomitant medication and treatment data for the historic control will be provided and summarized.

4.9.4 Safety data:

Safety data will be evaluated by changes in vital sign measurements, physical exam, laboratory analysis, and the frequency and severity of AEs. Concomitant medication will be recorded for safety.

Adverse events:

The Investigator is responsible for monitoring the safety of subjects who have enrolled in the study. All AEs considered related, or possibly related to Ampion™, will be followed until the event resolves or stabilizes without further change. Subjects will be followed for the occurrence of AEs until 12 weeks after the first dose of study medication.

Investigators are required to document all AEs occurring during the clinical trial, commencing with the first day of treatment through the end of study. AEs should be properly documented on the appropriate CRF pages.

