| 14.2.1.20 | Summary of PGA percent change |
| 14.2.1.21 | Summary of WOMAC mean change |
| 14.2.1.22 | Summary of WOMAC percent change |
| 14.3 Safety | |
| 14.3.1 | Overall Summary of TEAEs (Analysis Population: Safety) |
| 14.3.2 | Incidence of TEAEs by System Organ Class and Preferred Term (Analysis Population: Safety) |
| 14.3.3 | Incidence of Treatment Emergent Related AEs by System Organ Class and Preferred Term |
| 14.3.4 | Incidence of Treatment Emergent Serious AEs by System Organ Class and Preferred Term |
| 14.3.5 | Incidence of TEAEs by Preferred Term in Descending Order of Frequency |
| 14.3.6 | Incidence of Treatment Emergent Related AEs by Preferred Term in Descending Order of Frequency |
| 14.3.7 | Summary of Lab Value and Change from Baseline |
| 14.3.8 | Shifts in Reference Range |
| 14.3.9.1 | Summary of Vital Signs and Change from Baseline: Pulse (bpm) |
| 14.3.9.2 | Summary of Vital Signs and Change from Baseline: Temperature (°F) |
| 14.3.9.3 | Summary of Vital Signs and Change from Baseline: Systolic Blood Pressure (mmHG) |
| 14.3.9.4 | Summary of Vital Signs and Change from Baseline: Diastolic Blood Pressure (mmHG) |
| 14.3.10.1 | Concomitant Medication Use by ATC Level 1 and WHO Preferred Term |
| 14.3.10.2 | Medication started on study by ATC Level 1 and WHO Preferred Term |

| Number | Title |
|---------------------|---|
| 14.3.10.3 | Concomitant Medication Use by WHO Preferred Term in Descending Order of Use |
| 14.3.10.4 | Concomitant Medication Use by WHO Preferred Term in Descending Order of Use for Historic Control |
| 14.3.10.5 | Medication Started on Study by WHO Preferred Term in Descending Order of Use |
| 16- Listings | |
| 16.1 | Randomization List |
| 16.2 | Inclusion/Exclusion Criteria |
| 16.3 | Protocol Deviations |
| 16.4 | Early Terminations (Include date of ET and reason for ET) |
| 16.5 | Exclusions from PP |
| 16.6 | Demographics and Baseline Characteristics |
| 16.7 | Demographics and Baseline Characteristics for Historic Control |
| 16.8 | Medical History |
| 16.9 | Concomitant Medications |
| 16.10 | WOMAC/PGA/OMERACT OARSI Responder Status |
| 16.11 | Analgesic Used within 24 hours of visit |
| 16.12 | Adverse Events |
| 16.13 | Serious Adverse Events |
| 16.14 | Laboratory Values |
| 16.15 | Physical Exam (weight (lbs), Height, any abnormality (if listed)) and Vital Signs (BP, Temp, Pulse) |
| 16.16 | X-ray Data (and abnormalities, if listed) |

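### The planned physical-examination summary omits Week 6 and Early Termination and is specified only overall, and the SAP has no rule for Early Termination laboratory values

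*SAP*

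**What the plan says.** **Examinations.** SAP 4.9.2 gives the only analysis rule: "Results of any abnormalities documented from the abbreviated physical examination at Baseline and Week 12, will be summarized overall", for the safety and ITT populations. Protocol 10.3.11.2 has the same sentence. SAP 2.3 lists examinations at Baseline, Week 6 and Week 12 among the safety assessments. Protocol 5.1.5 instructs sites at Week 6: "Perform and record physical examination". Protocol Section 6 says the examination of the target knee looks for effusion and tenderness. SAP 7 states that outputs are shown by treatment arm, but its 14.3 list contains no examination table. Listing 16.15 covers examination abnormalities.

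**Laboratory tests.** SAP 2.3 gives the timing as "clinical laboratory tests (Screening and Week 12". Protocol 5.1.8 has at the Early Termination Visit: "Collect blood sample for laboratory assessment", and Protocol Table 6.1 marks it. The SAP Section 10 schedule leaves that cell blank.

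**Relatedness.** SAP 5.2 codes adverse events as unrelated, possibly related or related. Table 14.3.3 is titled "Incidence of Treatment Emergent Related AEs by System Organ Class and Preferred Term", and Table 14.3.6 shows the same class of events by frequency. Neither says whether possibly related events count. Protocol 9.3.1, on follow-up, treats as one group the events that are "drug-related (possibly related, definitely related".

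**The concern.** Safety is the trial's only stated secondary objective. The product is injected into the knee, so local findings on examination are an obvious place to look for a reaction. Visits 3 and 4 are telephone contacts, which makes Week 6 the first scheduled occasion after injection when anyone examines the joint. A summary limited to Baseline and Week 12 cannot show an effusion that came and went in between.

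The laboratory gap has the same character. The protocol schedules one post-injection blood draw, at Week 12. For a patient who leaves before then, the Early Termination sample may be the only post-injection value. If the programmer works from the SAP schedule, nothing prompts its inclusion.

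Timing also matters. SAP Section 1 says that analyses not specified in the SAP and performed after review of the data will be labelled post hoc. A Week 6 summary by arm added later would carry that label and would be a choice made with the data in view.

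**Working it through.** **The plan's own figure.** The only design calculation in the documents is the power statement. It has no bearing on this point but was checked. For the primary test the SAP states "The value will be 30% in this study. This test will be tested using an exact binomial test" and "Since this is a one-sided test, the alpha level will be 0.025". With n = 146, the smallest rejection count is 56:
- P(X ≥ 56 | 146, 0.30) = 0.0189, which is below 0.025.
- P(X ≥ 56 | 146, 0.45) = 0.956, so power above 90% is reproduced.

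**Collection against analysis.**

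| Assessment | Protocol Table 6.1 | SAP 2.3 | SAP 10 schedule | SAP analysis rule or output |
|---|---|---|---|---|
| Examination, Week 6 | yes | yes | yes | not in 4.9.2; Listing 16.15 only |
| Examination, Week 12 | yes | yes | yes | in 4.9.2; no 14.3 table |
| Examination, Early Termination | yes | not named | yes | not in 4.9.2; Listing 16.15 only |
| Laboratory, Week 12 | yes | yes | yes | Tables 14.3.7 and 14.3.8, no visit named |
| Laboratory, Early Termination | yes | not named | blank | Tables 14.3.7 and 14.3.8, no visit named |

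The examination rows show a stated rule that is narrower than the data collected. The last row shows a mismatch between schedules and a missing rule, not a stated exclusion.

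**Overall against by arm.** SAP 4.9.1 asks for demographics both overall and by treatment group, whereas 4.9.2 says only overall. SAP 7 says every table is by arm, but no examination table is listed for that rule to govern. If the arms were pooled, the pooled rate would be (146 × p_Ampion + 25 × p_saline) / 171, with weights 146/171 = 0.85 and 25/171 = 0.15. That single figure cannot show a difference between arms.

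**Size of the laboratory gap.** The documents give no dropout rate, so the rate d is an assumption. The number affected is 146 × d for Ampion and 25 × d for saline.

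| d | Ampion | saline |
|---|---|---|
| 2% | 2.9 | 0.5 |
| 5% | 7.3 | 1.25 |
| 10% | 14.6 | 2.5 |
| 20% | 29.2 | 5.0 |

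These are upper limits at each rate. They assume that every early leaver attends the visit and has blood drawn, but Protocol 7.2 counts loss to follow-up as withdrawal.

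**Relatedness.** No document splits related from possibly related events. Protocol Table 1.5.4 reports related events as one figure (63 of 907 saline, 73 of 932 Ampion). The effect of the definition on Tables 14.3.3 and 14.3.6 therefore cannot be computed.

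**The case against.** The strongest reply is that little is actually lost.

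- **Laboratory values.** SAP 4.10 counts everything collected under the protocol toward the safety assessment. Tables 14.3.7 and 14.3.8 and Listing 16.14 carry no visit limit. The two-visit wording in SAP 2.3 is shorthand that the protocol itself uses in its synopsis and Section 3.1. The blank cell sits in a schedule that also differs from the protocol on the screening window and visit numbers, so it looks like a transcription slip. This stands: a reader might infer that Early Termination laboratory values are excluded, and the documents do not say so. What remains is that no rule assigns them to an analysis visit.
- **Week 6 findings.** Protocol 9.3 allows an adverse event to be concluded from the physical examination, and adverse events are recorded at Week 6. A new effusion reported that way reaches the adverse-event tables. This also stands, and it limits the gap to findings not reported as adverse events. The restriction is in the protocol as well, so the SAP has not departed from the protocol's analysis section.
- **Pooling.** A reader might infer a settled plan to pool the arms. The by-arm statement in SAP 7 makes the wording ambiguous, so the documents do not support that.
- **Possibly related events.** A reader might infer that these are left out of the safety outputs. They are not: Tables 14.3.1, 14.3.2 and 14.3.5 and Listing 16.12 take adverse events whatever the relatedness. Only the word *related* in two tables is undefined.

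SAP 7 also refers to a separate document for the outputs. It is not among the documents reviewed and may settle some of these details.

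**Conclusion.** The examination point holds. SAP 4.9.2 states a rule that conflicts with the SAP's own list of safety examinations and sits awkwardly with its by-arm rule. With no examination table planned, a Week 6 finding that resolves by Week 12 and is not reported as an adverse event is seen only in a listing. The Early Termination laboratory mismatch is real, but it creates a risk of omission, not a stated omission. The relatedness point is a matter of definition only.

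A reader might go further and infer that these gaps flatter Ampion. The documents do not support that. The same rules apply to both arms, SAP 5.2 counts missing relatedness as related and missing severity as severe, and no figure shows a direction.

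The size is not known. The range of about 3 to 29 Ampion patients rests on an assumed 2% to 20% early termination with every leaver attending the visit, and would be realised only if their values were in fact left out of the tables. The primary result is not affected. This is a specification gap in the safety reporting that should be closed before unblinding.

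**What to change.** 1. In SAP 4.9.2 and Protocol 10.3.11.2, summarise examination abnormalities at Baseline, Week 6, Week 12 and Early Termination, by treatment arm, and add a 14.3 table for this, including the knee findings.
2. Reconcile the Early Termination laboratory cell in the SAP Section 10 schedule with Protocol 5.1.8 and Table 6.1. State that Tables 14.3.7 and 14.3.8 use the last post-injection value, from Week 12 or Early Termination.
3. As a wording clarification, state that *related* in Tables 14.3.3 and 14.3.6 means related plus possibly related, in line with Protocol 9.3.1.

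The cost is a few sentences in two documents, one added table and minor programming. No new data collection is needed. Reported counts of related events may rise compared with a table limited to the single *related* code.

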2.4 Sample Size

A total of approximately 171 subjects (146 Ampion; 25 Saline) will be enrolled in the study to a single (1) intra-articular injection of 4 mL Ampion or 4 mL saline (6:1).

The sample size for this study is based on the primary endpoint and is based on the following hypotheses.

$$H_0:\pi \leq 30\% \text{ versus } H_A:\pi > 30\%$$

A sample size of 146 patients in the active Ampion arm yields a greater than 90% power of rejecting the null hypothesis when the anticipated proportion under the alternative hypothesis is 45%. This power is applicable for the demonstration of an effect of at least some minimum size, defined in the current trial as greater than a 30% responder rate.

3. PRIMARY STUDY ENDPOINTS

3.1 Primary Endpoint

The primary trial endpoint is to evaluate improvement of OMERACT-OARSI response of a single 4 mL Ampion[™] intra-articular injection from Baseline to Week 12.

A patient in this study will be considered an OMERACT-OARSI responder for the purpose of efficacy analysis if the following criteria is met:

- 1) The patient has a percent improvement in pain (WOMAC pain) from baseline of $\geq 50\%$ and an absolute change in pain from baseline of ≥ 1 point or the patient has a percent improvement in function (WOMAC function) from baseline of $\geq 50\%$ and an absolute change in function from baseline of ≥ 1 point. Meeting this criterion designates the patient as a responder. If the patient does not meet this criterion, then
- 2) The patient demonstrates improvement in at least 2 of the following:
 - Improvement in pain (WOMAC A) over baseline of $\geq 20\%$ and a 0.5 point absolute change in pain
 - Improvement in function (WOMAC function) over baseline of $\geq 20\%$ and a 0.5 point absolute change in function
 - Improvement in patient global assessment (PGA) over baseline of $\geq 20\%$ and a 0.5 point absolute change in PGA

3.2 Secondary Endpoints

The secondary trial endpoints are to evaluate improvement in a composite endpoint of pain and function, defined as OMERACT-OARSI “controlled” responder, supported by patient global assessment following a single 4 mL Ampion intra-articular injection from Baseline to Week 12.

Secondary endpoints are to evaluate improvement of:

- OMERACT-OARSI “controlled” response from Baseline to Week 12
- PGA response from Baseline to Week 12
- OMERACT-OARSI “controlled” responder from Baseline to Week 12 in comparison to historic saline

A patient in this study will be considered an OMERACT-OARSI “controlled” responder for the purpose of efficacy analysis if the following criteria is met:

- 1) The patient demonstrates improvement in both:
 - Improvement in pain (WOMAC A) over baseline of $\geq 20\%$ and a 0.5 point absolute change in pain
 - Improvement in function (WOMAC function) over baseline of $\geq 20\%$ and a 0.5 point absolute change in function

A patient in this study will be considered to have a PGA response if the following criteria is met:

- Improvement in patient global assessment (PGA) over baseline of $\geq 20\%$ and a 0.5 point absolute change in PGA

4. HYPOTHESES AND METHODS

4.1 Primary Hypothesis

Demonstration of an effect of at least some minimum size is considered essential for acceptance of efficacy, and this is defined in the current trial as a greater than 30% responder rate based on review of KOL opinion, literature, and clinical benefit in severely diseased OAK patients. For the primary endpoint of the proportion of patients who are responders to the OMERACT-OARSI criteria from above, the following hypothesis will be tested.

$$H_0:\pi \leq \pi_0 \text{ versus } H_A:\pi > \pi_0$$

Where π_0 is the hypothesized clinically significant value for the proportion of responders. The value will be 30% in this study. This test will be tested using an exact binomial test. That is, given the sample size of n , the number of responders X , and the value of $\pi_0 = 0.30$, then probability that X or more events would be observed will be calculated as the p -value. Since this is a one-sided test, the alpha level will be 0.025.

4.2 Secondary Hypotheses

The primary hypothesis and these secondary hypotheses will be tested in a hierarchical manner with the primary first and the secondary hypotheses in the order listed. Using this approach, there is no adjustment necessary in the overall significance level. All testing will be conducted using an overall significance level of 5%. If the tests are one sided, the significance level will be 2.5%.

For the secondary endpoint of the proportion of patients who are “controlled responders” to the OMERACT-OARSI criteria as defined in section 3.2 above, the following hypothesis will be tested.

$$H_0:\pi \leq \pi_0 \text{ versus } H_A:\pi > \pi_0$$

Where π_0 is the hypothesized clinically significant value for the proportion of responders. The value will be 30% in this study. This test will be tested using an exact binomial test. That is, given the sample size of n , the number of responders X , and the value of $\pi_0 = 0.30$, then probability that X or more events would be observed will be calculated as the p -value. Since this is a one sided test, the alpha level will be 0.025.

This composite analysis of OMERACT-OARSI “controlled responder” will be supported by Patient Global Assessment. Patient Global Assessment will be tested against the same hypothesis:

$$H_0:\pi \leq \pi_0 \text{ versus } H_A:\pi > \pi_0$$

The 3rd secondary trial endpoint, evaluating the improvement in a composite endpoint of pain and function (WOMAC A and C), defined as OMERACT-OARSI “controlled” response, will demonstrate that the active arm from this study is superior to analysis of all

historic saline-control arms from previous single-injection Ampion studies, will be analyzed using the following hypothesis.

$$H_0: \pi_A \leq \pi_{HS} \text{ versus } H_A: \pi_A > \pi_{HS}$$

Where π_A is the response rate from Ampion in this study and π_{HS} is the response rate of the saline control from previous single-injection Ampion studies. This will be tested using Fisher's exact test.

4.3 Exploratory Analysis

If it is deemed to be clinically relevant, the analyses will be conducted using the appropriate adjustment methodologies.

4.4 Definition of Study Visits

This clinical trial has a total of 7 study visits during the 12-week study (see Table 6.2). The time on study for each subject observation will be defined relative to Day 0/Baseline, the day of the initial dose. For analysis, the Baseline measure is the latest measure prior to initiation of treatment.

4.5 Number of subjects to receive study drug

A total of approximately 171 subjects (146 Ampion; 25 Saline) will be enrolled in the study to a single (1) intra-articular injection of 4 mL Ampion or 4 mL saline (6:1).

4.6 Disposition of subjects

Disposition of subjects, including study completion status and response to therapy as measured by WOMAC subscores and PGA, will be summarized by age group, race, and gender for each of the analysis populations.

4.7 Interim analysis

There will be no interim analysis.

4.8 Blinding and randomization

All subjects will be randomized 6:1 to receive Ampion 4 mL or saline 4 mL as an intra-articular injection in the study knee.

4.9 Data presentation

4.9.1 Demographic and Baseline Characteristics:

Demographic (e.g., age, sex, race, and ethnicity) and Baseline characteristics (e.g., weight, height, prior injection of another intra-articular therapeutic for OA of the knee) will be summarized using descriptive statistics, overall and by treatment group for the ITT analysis population. Demographic data for the historic control will be provided and summarized.

4.9.2 Medical History and Physical Examination:

The number and percent of subjects with past and current medical disorders at the time of randomization will be presented overall for the ITT analysis population. Results of any abnormalities documented from the abbreviated physical examination at Baseline and Week 12, will be summarized overall for the safety and ITT analysis populations.

4.9.3 Concomitant Medications or Treatments:

The number and percent of subjects receiving concomitant medications or treatments prior to and during the study and at the final visit will be tabulated and presented overall for the ITT analysis population. Concomitant medications/treatments will be summarized using descriptive statistics and will be presented by type of drug (WHO DRUG classification) overall for the safety and ITT analysis populations. Concomitant medication and treatment data for the historic control will be provided and summarized.

4.9.4 Safety data:

Safety data will be evaluated by changes in vital sign measurements, physical exam, laboratory analysis, and the frequency and severity of AEs. Concomitant medication will be recorded for safety.

Adverse events:

The Investigator is responsible for monitoring the safety of subjects who have enrolled in the study. All AEs considered related, or possibly related to Ampion™, will be followed until the event resolves or stabilizes without further change. Subjects will be followed for the occurrence of AEs until 12 weeks after the first dose of study medication.

Investigators are required to document all AEs occurring during the clinical trial, commencing with the first day of treatment through the end of study. AEs should be properly documented on the appropriate CRF pages.

The severity of AEs (mild, moderate, severe), relatedness (related, possibly related, unrelated) along with the duration, action taken, and outcome (e.g., study withdrawal) will also be recorded. In addition, events meeting the criteria of a Serious Adverse Event (SAE) must be reported to the Sponsor within 24 hours on the SAE reporting forms.

